Effect of rasagiline on balance in Parkinson's disease as measured by computerized posturography

[name]

Approved: 9/15/2014

Department of Neurology

New York Medical College, Valhalla, NY

United States of America

Corresponding Author

[name]

[name]

[name]

United States of America

[contact]

[contact]

Email: [contact]

Keywords: rasagiline, balance, posturography, Parkinson's disease

Abstract:**Background:**

Falls occur in a majority of Parkinson's disease (PD) patients. Balance disturbance can be measured by computer dynamic posturography. The effect of monoamine oxidase inhibition on PD patients as measured by computer dynamic posturography has not been previously studies.

Methods:

The study will test the hypothesis that therapy with rasagiline improves balance in PD patients as measured by computerized dynamic posturography. 5 subjects will be randomized to rasagiline or placebo and 5 further subjects will be randomized to rasagiline as adjuvant therapy versus placebo. Subjects will be analyzed by computerized dynamic posturography testing. The device measures body sway under varying visual and vestibular cues and is used for assessment of balance. Subjects will be evaluated at baseline prior to taking first tablet as well as at 4 weeks and 8 weeks. In the adjuvant therapy arm, subjects will be evaluated on rasagiline but in a functional OFF state for their other PD medications. If the scores are normally distributed, we will determine whether data variance is approximately equal in all tested groups. If these conditions are met, data evaluation will continue using repeated measures ANOVA with between factor of drug (levels: rasagiline, placebo) and within factor of treatment (levels: before, after). Level of significance will be preset to 0.05.

Background:

Posturography testing for Parkinson's disease patients on monoamine oxidase (MAO) inhibitors in general has not been studied previously. In Wood's study of patients with Parkinson's disease, falls occurred in 68.3% of the subjects [1]. In Ebmeier's population study of idiopathic Parkinson's disease patients, signs of postural instability on clinical examination were among the factors listed in premature death [2].

Hypothesis

The hypothesis is that therapy with rasagiline improves balance in PD patients as measured by computerized dynamic posturography.

Methods:**Inclusion Criteria:**

1. 18 years old or above
2. Clinical diagnosis of Parkinson disease by verified by movement disorders expert at the initial study visit with at least two cardinal signs of the disease (rest tremor, bradykinesia, rigidity, and postural instability).
3. For the monotherapy arm, patients must not be on amantadine, dopamine agonists, or levodopa. For the adjuvant therapy arm: Patients must be on a stable dose of their current medication for treatment of Parkinson disease which may include any combination of the following: amantadine, trihexiphenydil, dopamine agonist, and/or levodopa.
4. Patients may continue their stable dose of tricyclic, selective serotonin reuptake inhibitor, or serotonin norepinephrine reuptake inhibitor if they are on these medications at randomization.

Exclusion Criteria:

1. Catechol-O-Methyltransferase (COMT) inhibitor therapy use 30 days prior to start of study (both study arms).
2. Dopamine receptor blocker use (such as quetiapine) one week prior to taking study drug
3. For both monotherapy and adjuvant therapy arms: use of MAO inhibitor therapy including selegiline or rasagiline within 30 days prior to taking study drug and first posturography evaluation.

Study Visits:**Screening:**

Patients will be evaluated by movement disorders expert who will confirm diagnosis of Parkinson disease as stipulated in inclusion criteria. Blood pressure and heart rate, as well as a complete Unified Parkinson Disease Rating Scale (UPDRS) evaluation will be performed.

Randomization:

Subjects will be randomized by facility pharmacy to either placebo or rasagiline 1 mg daily for 8 weeks. There will be 5 rasagiline monotherapy and 5 matching placebo subjects as well as 5 rasagiline adjuvant therapy and 5 matching placebo subjects.

Computerized dynamic posturography evaluation:

Subjects will be evaluated at baseline prior to taking first tablet as well as at 4 weeks and 8 weeks. In the adjuvant therapy arm, subjects will be evaluated on rasagiline but in a functional OFF state for their other PD medications.

Functional OFF will be defined as at least 24 hours post last dose of long acting dopamine agonist or levodopa extended or continuous release formulations, at least 8 hours post last dose of immediate release dopamine agonist, immediate release levodopa, or trihexyphenidyl.

Subjects will undergo computerized dynamic posturography testing via apparatus manufactured by Neurocom, Inc. This device is clinically used for measurement of balance impairment. It measures body sway under varying visual and vestibular cues [3]. Motor control test (MCT) measuring body sway during small translations of the support surface will also be used.

Conclusion of study:

Subjects will stop taking rasagiline or placebo once their 8 week supply runs out.

Power analysis to determine the number of subjects

To estimate number of subjects needed for the posturography test, we performed a power analysis using the software G*power [4]. For inputs, data from the effect of dopamine depleter tetrabenazine on posturography in Huntington's disease was used [5].

The strategy composite score here during the tetrabenazine ON state was 79.2, during tetrabenazine OFF state it was 63.5. Averaged SD for these two outcomes was 11.5 and the total sample size was 10. These data were used to calculate the anticipated effect size. This input provided the Effect Size $f = 0.6826087$ (Table 1).

Input of the effect size value into the G*power with requested $\alpha=0.05$ and power $(1-\beta)=0.9$, weighing in the repeated measurements (before and after rasagiline) with very low correlation among repeated measures resulted in returned total sample size of 10 subjects Table 1 (please see the table of calculated inputs and outputs below). This total number will be randomized into 2 groups of subjects: rasagiline monotherapy and placebo study arm. Similarly, there will be 10 subjects in the study arm with rasagiline as an adjuvant therapy versus placebo.

F tests - ANOVA: Repeated measures, between factors

Analysis: A priori: Compute required sample size

Input:	Effect size f	=	0.6826087
	α err prob	=	0.05
	Power ($1-\beta$ err prob)	=	0.9
	Number of groups	=	2
	Repetitions	=	4
	Corr among rep measures	=	.1
Output:	Noncentrality parameter λ	=	14.337066
	Critical F	=	5.317655
	Numerator df	=	1.000000
	Denominator df	=	8.000000
	Total sample size	=	10
	Actual power	=	0.910691

Table 1. G*power software inputs and outputs for statistical power

General approach for statistical evaluation of the study data

The output of the posturography testing are computer-calculated scores. Though these scores are discrete (do not represent a continuous variable), they still may fit the requirements of parametric statistical tests. Thus, we will first test the raw scores for normal distribution using a Kolmogorov-Smirnov test versus dataset with known Gaussian distribution. If the scores are normally distributed, we will determine whether data variance is approximately equal in all tested groups. If these conditions are met, we will continue data evaluation using repeated measures ANOVA with between factor of drug (levels: rasagiline, placebo) and within factor of treatment (levels: before, after). Level of significance will be preset to 0.05. Since no multiple comparisons are planned, there will be no adjustments of p.

If we do not find the Gaussian distribution of scores or if the variances among the groups are unequal (difference of one order of magnitude or more), we will calculate non-parametric statistics to determine differences. For this purpose we will use Wilcoxon Signed Rank test and evaluate separately rasagiline and placebo groups with p preset to 0.05.

Abbreviations

COMT: Catechol-O-Methyltransferase

HD: Huntington's disease

MCT: Motor control test

PD: Parkinson's disease

References:

1. Wood BH, Bilclough, Bowron A. Incidence and prediction of falls in Parkinson's disease: a prospective multidisciplinary study. *J Neurol Neurosurg Psychiatry* 2002;72:721-725
5. [name], Davidson, A., Ondo, W.G., and Cohen, H.S. Effect of tetrabenazine on computerized dynamic posturography in Huntington disease patients. *Parkinsonism and Related Disorders* 2012;18(7):896-8.

Declarations**Ethics Approval and Consent to Participate**

The study was not registered as no patients were enrolled. The study was approved by the New York Medical College Office of Research Administration Institutional Review Board under tracking number L-10,768.

Consent for Publication

Not applicable

Competing Interests

RF has served as a consultant for Teva Neuroscience, Inc.

Funding

There was no funding for this study.

Author Contributions

RF Conception, writing of manuscript.

Data Availability

Given the absence of funding, data gathering could not commence. No data was gathered.

Acknowledgements

None

Figure Legends

Table 1. G*power software inputs and outputs for statistical power

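### Inclusion criterion 3 omits trihexyphenidyl from the monotherapy bar, although the protocol lists it as Parkinson's medication and requires at least 8 hours off it before testing in the adjuvant cohort

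*Combined protocol and SAP*

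**What the plan says.** The protocol runs two randomised comparisons of rasagiline with placebo, one as monotherapy and one as adjuvant therapy, each with 5 subjects per arm. It uses the word arm for both divisions. Here cohort means monotherapy or adjuvant, and arm means rasagiline or placebo.

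Four places bear on the point:

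- Inclusion Criteria, item 3, monotherapy cohort: "For the monotherapy arm, patients must not be on amantadine, dopamine agonists, or levodopa".
- Inclusion Criteria, item 3, adjuvant cohort: patients must be on a stable dose of current Parkinson's medication, "which may include any combination of the following: amantadine, trihexiphenydil, dopamine agonist, and/or levodopa".
- Computerized dynamic posturography evaluation: "In the adjuvant therapy arm, subjects will be evaluated on rasagiline but in a functional OFF state for their other PD medications". Functional OFF is then defined by time since last dose, including "at least 8 hours post last dose of immediate release dopamine agonist, immediate release levodopa, or trihexyphenidyl".
- Inclusion Criteria, item 4, on antidepressants: "Patients may continue their stable dose of tricyclic, selective serotonin reuptake inhibitor, or serotonin norepinephrine reuptake inhibitor".

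The planned analysis, under the general approach for statistical evaluation, is a "repeated measures ANOVA with between factor of drug (levels: rasagiline, placebo) and within factor of treatment (levels: before, after". If normality or equal variance fails, the fallback is a Wilcoxon signed rank test run separately in the rasagiline and placebo groups.

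**The concern.** The protocol treats trihexyphenidyl as a Parkinson's drug and treats recent dosing as relevant to posturography, but applies both ideas in one cohort only. The monotherapy criterion is a closed list of three drugs, and trihexyphenidyl is not on it. A patient taking only that drug meets the criterion as written.

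Two things are at stake. First, the monotherapy cohort is meant to show what rasagiline does alone, and such a patient may be tested while on another Parkinson's drug. Second, nothing in that cohort fixes the dose or the time from dose to test. If either differs between baseline and a later visit, the difference is recorded as change over the treatment period.

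**Working it through.** **Step 1: set the rules side by side.** The two spellings in the protocol are read as the same drug.

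| Drug | Monotherapy cohort | Adjuvant cohort | Minimum time off before testing (adjuvant only) |
|---|---|---|---|
| Amantadine | barred | stable dose | none stated |
| Dopamine agonist | barred | stable dose | 24 h long acting, 8 h immediate release |
| Levodopa | barred | stable dose | 24 h extended or continuous release, 8 h immediate release |
| Trihexyphenidyl | not barred, no dose rule, no time off | stable dose | 8 h |

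Three of the four listed drugs are barred from monotherapy. The fourth is neither barred nor controlled.

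**Step 2: look for another criterion that closes the gap.** Exclusion 1 covers COMT inhibitors, exclusion 2 dopamine receptor blockers, and exclusion 3 MAO inhibitors. Inclusion 4 concerns antidepressants. None covers trihexyphenidyl. Inclusion 4 also shows that the protocol normally attaches a stable-dose condition to a permitted background drug.

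**Step 3: follow the drug into the before-after contrast.** Let h be what trihexyphenidyl adds to a subject's score at a visit.

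- Contribution to that subject's change = h(after) − h(before).
- Stable use with a constant effect: h − h = 0.
- Dose or timing differs, so that h changes by δ: the contribution is δ. With 5 subjects per arm, that arm's mean change moves by δ/5 = 0.2δ.
- The difference between arms moves by +0.2δ if the subject is on rasagiline and −0.2δ if on placebo. With equal chances of either, the average is ½(0.2δ) + ½(−0.2δ) = 0, provided δ does not depend on the assigned arm.

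The Wilcoxon fallback is also paired, so a constant effect cancels there too. A change δ does not cancel, and that fallback has no between-arm comparison to set it against.

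The documents give no value for δ, not even its sign, and no expected number of such patients. The calculation stops at 0.2δ per affected subject in an arm.

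**Step 4: check whether the power figure is involved.** Table 1 reproduces:

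- f = (79.2 − 63.5)/(2 × 11.5) = 15.7/23 = 0.6826
- λ = f² × N × m/(1 + (m − 1)ρ) = 0.6826² × 10 × 4/(1 + 3 × 0.1) = 14.337
- With critical F(1, 8) = 5.318, power = 0.911, as printed.

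None of these inputs depends on the list of barred drugs, so correcting the list changes no sample size, power or significance level.

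**The case against.** **The cohort's name settles it.** Monotherapy is set against adjuvant therapy throughout, the next sentence of inclusion 3 gives a stable trihexyphenidyl user a place in the adjuvant cohort, and a movement disorders expert sees every patient at screening. This is good evidence of intent, and it makes misplacement less likely. But if the name were enough, the other three drugs would not need listing. The expert's stated task at screening is to confirm the diagnosis, not to choose the cohort.

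**The 8-hour comparison is selective.** Amantadine is on the adjuvant list yet has no interval in the functional OFF definition, so the protocol does not withhold every listed drug. That is true, and it weakens any argument from the missing interval alone. It does not explain why amantadine is barred from monotherapy and trihexyphenidyl is not.

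**One added name leaves a closed list.** A Parkinson's drug outside the four names and the exclusions would still be admitted. This stands as a limit of the fix, which removes the inconsistency visible in the text and no more.

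**Nobody was affected.** The declarations say that no patients were enrolled and no data gathered. The point therefore matters only if the protocol is used or reused.

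**A stronger reading that a reader might infer** is that the omission costs the trial a definite amount of power. One could assume a constant shift in one subject and recompute Table 1's between-factor test, where such a shift does not cancel within a single trial. The documents do not support this. They give no number of users and no size or direction of effect. The 15.7-point difference comes from tetrabenazine in Huntington's disease and sets no limit on the effect of another drug. A constant shift is also the case that cancels before versus after, whereas the hazard left open is a changing dose or timing. No power loss is claimed here.

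**Conclusion.** The point holds as a minor inconsistency in the eligibility rule. As written, inclusion 3 admits to the monotherapy cohort a patient on a drug that the protocol itself classes as Parkinson's medication, with neither the stable-dose condition nor the 8-hour interval that the adjuvant cohort applies to it.

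Its effect cannot be quantified from the documents. It is zero in the before-after contrast if use is stable and the effect constant, and it averages to zero over random allocation if changes in dosing are unrelated to the assigned arm. What remains is that changing use in one subject could move an arm's mean change in a given trial, and that the cohort would not strictly test rasagiline alone. Both depend on at least one trihexyphenidyl-only patient being enrolled under a literal reading of the criterion. A reader might go further and infer that the randomised comparison is biased; the documents give no ground for that.

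**What to change.** In inclusion criterion 3, add trihexyphenidyl to the drugs barred from monotherapy, so that the list reads amantadine, trihexyphenidyl, dopamine agonists and levodopa and matches the adjuvant list. Patients on a stable dose of trihexyphenidyl alone then enter the adjuvant cohort, where they already qualify and the 8-hour rule already applies.

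The change is one drug name. The design and analysis stay as they are. The one downside is that a patient on an unstable trihexyphenidyl dose, who is eligible for monotherapy under the present wording, would fit neither cohort and must wait until the dose is stable.

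### Table 1 enters four repetitions, but the plan describes two or three measurements, so the stated power of 0.91 at 10 per cohort does not belong to the described design

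*Combined protocol and SAP*

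**What the plan says.** The document gives three different counts of repeated measurements.

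- **Two, in the power text.** The section on the power analysis describes "weighing in the repeated measurements (before and after rasagiline) with very low correlation among repeated measures" and reports that this "resulted in returned total sample size of 10 subjects".
- **Two, in the analysis.** The general approach to statistical evaluation specifies a "within factor of treatment (levels: before, after". The abstract repeats it: "data evaluation will continue using repeated measures ANOVA with between factor of drug (levels: rasagiline, placebo) and within factor of treatment (levels: before, after".
- **Three, in the schedule.** The section on the posturography evaluation states: "Subjects will be evaluated at baseline prior to taking first tablet as well as at 4 weeks and 8 weeks".
- **Four, in Table 1.** The G*Power procedure is "ANOVA: Repeated measures, between factors", with "Repetitions = 4", two groups, correlation 0.1, alpha 0.05 and requested power 0.9. The output is a total of 10 subjects and "Actual power = 0.910691".

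The Randomization section allots 5 rasagiline and 5 placebo subjects to each of the monotherapy and adjuvant cohorts, so 10 is the total per cohort.

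**The concern.** In the between-factors procedure, each extra repetition reduces the variance of a subject's average and so raises the power. With a correlation as low as 0.1 the gain is large. Entering four therefore credits the design with measurements that the plan does not describe.

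Table 1 is the only justification given for 10 subjects per cohort. If its power figure rests on an unsupported input, the claim that the requested 0.90 is met fails too. Anyone reusing this public plan would inherit the figure.

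**Working it through.** **Inputs.** The power section gives means of 79.2 and 63.5 (difference 15.7) and an averaged SD of 11.5. Table 1 gives 2 groups, correlation rho = 0.1, alpha = 0.05 and N = 10. Let m be the number of repeated measurements.

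**Effect size.** f = (79.2 − 63.5) / (2 × 11.5) = 0.6826087, as printed; f² = 0.46595.

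**Formula.** For this procedure, lambda = f² × N × m / (1 + (m − 1) × rho). Power is the probability that a noncentral F with 1 and N − 2 = 8 degrees of freedom exceeds the critical value 5.317655.

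**Plan's own figure, m = 4.** lambda = 4.65955 × 4 / 1.3 = 14.337066 and power = 0.910691. Both agree with Table 1 to the last printed digit. The 4 was therefore used in the calculation and is not a misprint.

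**Changing only m:**

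| m | lambda | Power | Type II error |
|---|---|---|---|
| 4 (Table 1) | 4.65955 × 4 / 1.3 = 14.337 | 0.911 | 0.09 |
| 3 (schedule) | 4.65955 × 3 / 1.2 = 11.649 | 0.847 | 0.15 |
| 2 (power text, ANOVA) | 4.65955 × 2 / 1.1 = 8.472 | 0.723 | 0.28 |

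Entering 4 inflates lambda by 69% against m = 2 (14.337 / 8.472 = 1.692) and by 23% against m = 3 (14.337 / 11.649 = 1.231).

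**Sensitivity to the correlation.** The plan gives only 0.1; the other values are assumptions.

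| rho | 0 | 0.1 | 0.3 | 0.5 | 0.7 |
|---|---|---|---|---|---|
| m = 2 | 0.76 | 0.72 | 0.65 | 0.59 | 0.54 |
| m = 3 | 0.90 | 0.85 | 0.74 | 0.64 | 0.56 |

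Power of 0.90 at N = 10 needs lambda = 13.782. With m = 3 that holds only for rho up to about 0.007. With m = 2 it fails even at rho = 0.

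**Size of the shortfall in points.** At rho = 0.1, solving lambda = 13.782 for f gives 0.7425 (m = 3) or 0.8706 (m = 2). Multiplied by 2 × 11.5, these are differences of 17.1 or 20.0 points, against the 15.7 used.

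**What the procedure assumes about baseline.** The calculation takes the 15.7-point difference as present at every measurement, although baseline precedes the first tablet. If the difference exists only after treatment (an assumption), the averaged effect shrinks to 1/2 (m = 2) or 2/3 (m = 3). At N = 10 and rho = 0.1:

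- m = 2: lambda = 8.472 / 4 = 2.118, power 0.25.
- m = 3: lambda = 11.649 × 4/9 = 5.177, power 0.52.
- Comparison of before-after change: SD of change = 11.5 × √(2 × 0.9), lambda = 2.589, power 0.29.

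**What Table 1's procedure would return.** With Repetitions corrected and rho = 0.1, the smallest even total reaching 0.90 is 12 for m = 3 (0.919) or 16 for m = 2 (0.928). These show that the stated basis for 10 depends on the erroneous input. They are not recommended sizes: under the post-treatment-only assumption, between-factors power there is only 0.61 and 0.40.

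**The case against.** The mismatch and the arithmetic are hard to dispute. The stronger objections concern what follows from them.

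- **0.72 and 0.85 are not the trial's true power either.** They inherit the assumption of a full difference at baseline, and the choice of a between-factors test may cost more power than the Repetitions entry. This stands. The figures should be read only as Table 1's procedure with one input corrected.
- **The correlation can help as well as hurt.** For a comparison of before-after change, power rises with correlation: 0.29 at 0.1, 0.48 at 0.5, 0.69 at 0.7 and 0.85 at 0.8 (all but 0.1 assumed). This is true and should be shown, but that is not the calculation in Table 1, and none of these values reaches 0.90.
- **Another procedure reaches the target.** The within-between interaction option with the same f, rho and N gives 0.903 at m = 3. That is neither the procedure run nor the planned two-level factor; with two levels it gives 0.804.
- **Four may mean two groups by two times.** The document does not say so, and the groups already have their own line in Table 1, so this would count them twice.
- **Three visits need not contradict a before/after factor.** The after level could be week 8 or an average of weeks 4 and 8. That is fair: the level is undefined. No reading of it yields four.
- **No data were gathered.** This is correct, and it limits the consequence to the plan itself.

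**Conclusion.** The concern holds and should be fixed. Table 1's Repetitions entry agrees with neither the power text, the ANOVA nor the visit schedule, and no other part of the document supports it. On Table 1's remaining inputs (f 0.6826, correlation 0.1, alpha 0.05, N = 10 per cohort), power is 0.72 for two measurements or 0.85 for three. The claim of at least 0.90 is therefore not supported.

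The verdict on the input does not depend on any outside assumption. The size does: it takes the plan's effect size and correlation as given and accepts the full difference at baseline. Dropping that last assumption lowers the figures further, but this is a separate weakness and is not needed for the conclusion. The Data Availability statement says that no data were collected, so no trial result is affected.

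**What to change.** 1. Make the schedule, the ANOVA levels and Table 1 agree on one number of measurements. Either define which visit or summary is the after level (two measurements), or model all three visits.
2. Correct Repetitions and rerun the calculation. Replace 0.910691 and the claim of 0.90 power with the recomputed figure for 10 per cohort (0.72 for two, 0.85 for three, at correlation 0.1), shown over a range of correlations and labelled as the between-factors procedure with corrected input.
3. State beside it that this procedure assumes the full 15.7-point difference at baseline as well. Report the power if the difference is post-treatment only, marked as an assumption.

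The cost is one G*Power rerun, one definition or one added ANOVA level, and a few corrected sentences. No change in sample size is asked for. The drawback is that the plan will show less favourable power than it now claims, and it will have to acknowledge that its 0.90 target is not met.

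### Table 1's power of 0.91 is for a between-factor test with four repetitions and an unsourced correlation of 0.1; on the plan's own inputs the planned before/after comparison has power of about 0.29 to 0.37

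*Combined protocol and SAP*

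**What the plan says.** The section on the power analysis takes its effect from a study of tetrabenazine in Huntington's disease: "The strategy composite score here during the tetrabenazine ON state was 79.2, during tetrabenazine OFF state it was 63.5". It adds: "Averaged SD for these two outcomes was 11.5 and the total sample size was 10". These figures give an effect size f of 0.6826087.

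Table 1 names the procedure as "F tests - ANOVA: Repeated measures, between factors". The inputs are alpha 0.05, power 0.9, two groups, four repetitions and a correlation of 0.1. The output is a total of 10 subjects, a noncentrality of 14.337066 on 1 and 8 degrees of freedom, and a power of 0.910691. The text says only that the input "with very low correlation among repeated measures resulted in returned total sample size of 10 subjects". It gives no source, reason or sensitivity range for that correlation. The same number is then used for the monotherapy and the adjuvant sub-study, each split 5 against 5.

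Under Study Visits, posturography is done three times: before the first tablet, at 4 weeks and at 8 weeks. The general approach to the analysis is a repeated measures ANOVA with drug as the between factor and a "within factor of treatment (levels: before, after". The text does not say how the two post-treatment visits form the second level.

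**The concern.** In a between-factor test the subject's repeats are averaged. The lower their correlation, the closer each repeat comes to counting as a new subject. A value of 0.1 is therefore near the favourable end for the test in Table 1. It is the opposite for a before/after comparison, which gains precision only when a subject's two scores are closely related.

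The planned analysis contains a before/after factor, and the baseline precedes the first dose. Randomised groups should not differ at baseline except by chance, so the effect of the drug is the difference between the groups in their change, which is the interaction. Table 1 powers a different test, and does so with more repetitions than either the schedule or the analysis contains.

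A null result from 10 subjects would be read as coming from a trial with 90% power, although on the plan's own inputs the relevant comparison had about a third of that.

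**Working it through.** **Inputs.** Difference 79.2 − 63.5 = 15.7; SD 11.5; f = 15.7 / 11.5 / 2 = 0.6826, so f² = 0.46595; N = 10 (5 v 5); alpha 0.05; rho = 0.1; m = 4. All are from the power section, Table 1 and the randomisation section. The critical F on 1 and 8 degrees of freedom is 5.3177.

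**1. The plan's own figure.** Between factor: λ = f² N m / (1 + (m − 1) rho) = 0.46595 × 10 × 4 / 1.3 = 14.337. The noncentral F gives power 0.9107. Table 1 reproduces exactly.

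**2. Sensitivity to rho, with m still 4.** Power of 0.90 on 1 and 8 degrees of freedom needs λ of about 13.78. Setting 18.638 / (1 + 3 rho) = 13.78 gives rho ≈ 0.117. At rho 0.2 the power is already 0.847. These figures show the sensitivity of Table 1 only. They are not the power of this trial, because m = 4 matches no schedule in the plan.

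**3. Repetitions that match the plan, with rho still 0.1.**
- m = 3 (three assessments): λ = 13.979 / 1.2 = 11.649, power 0.847.
- m = 2 (before, after): λ = 9.319 / 1.1 = 8.472, power 0.723. Even at rho = 0 it is only 0.762.

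These values are still generous, because they assume the full 15.7 at every repetition, including baseline. If the groups are equal at baseline, the difference averaged over before and after is 7.85. Then f = 0.3413, λ = 0.1165 × 10 × 2 / 1.1 = 2.118, and the main-effect power is 0.25.

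**4. The drug-by-treatment interaction.** Compare change between groups, 5 v 5, with λ = (15.7² / variance of change) × (5 × 5 / 10). Take SD 11.5 at each visit and a group difference in change of 15.7.
- One post-treatment visit: variance of change = 11.5² × 2(1 − rho). At rho 0.1, λ = 246.49 / (132.25 × 1.8) × 2.5 = 2.589, power 0.29.
- Mean of weeks 4 and 8, assuming equal correlations and the full effect at both visits: variance = 11.5² × 1.5(1 − rho). At rho 0.1, λ = 246.49 / (132.25 × 1.35) × 2.5 = 3.452, power 0.37.

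Over a range of rho (an assumption, since the documents give no range):

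| rho | one post visit | mean of two |
|---|---|---|
| 0.1 | 0.29 | 0.37 |
| 0.5 | 0.48 | 0.59 |
| 0.7 | 0.69 | 0.80 |
| 0.8 | 0.85 | 0.93 |

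**5. Where the interaction reaches 0.90.** With λ = 13.78 and (15.7 / 11.5)² = 1.8638, one post visit needs 1 − rho = 2.5 × 1.8638 / (2 × 13.78) = 0.169, so rho is about 0.83. The mean of two needs 1 − rho = 2.5 × 1.8638 / (1.5 × 13.78) = 0.225, so rho is about 0.77.

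**The case against.** The strongest reply is that nothing here is a miscalculation: Table 1 reproduces to every digit, and the low correlation is disclosed in both text and table. That stands. The fault lies in the choice of test and inputs.

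A second reply is that the documents hold no test-retest correlation for posturography, so nobody can say that 0.1 is wrong. That also stands, and it limits the point. A reader might infer that 10 subjects fail at ordinary correlations, with 0.5 to 0.8 as the ordinary range. The documents do not support this, and the range is used here only for illustration. Nor does a low correlation contradict the use of the score as an outcome; it implies a noisy measure and no more.

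A reader might also infer that no correlation can rescue the plan, because low values weaken the interaction and high values weaken the between-factor test. That is not so. Interaction power is 0.93 at rho 0.8 with the mean of two post visits, and 0.93 at 0.85 with one.

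Finally, the repetitions input breaks the 0.9 claim without any change to rho, so the correlation is not the only cause. That is correct, and both need correcting together. The declarations also state that no patients were enrolled, so no actual result has been misread. The harm would arise if the plan were funded or reused.

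**Conclusion.** The point holds as a mismatch between the power claim and the planned analysis, not as an arithmetic error. The 0.91 belongs to a between-factor test with four repetitions at an unsourced correlation that favours it. With the plan's own difference, SD, correlation and group sizes, the before/after drug effect has power of about 0.29 or 0.37, depending on how the post-treatment visits are combined.

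These two figures rest on an SD of 11.5 at every visit and a group difference in change of 15.7. The second also assumes equal correlations and the full effect at both post visits. They make no allowance for dropout, and none is stated in the plan. Whether 10 subjects per sub-study are enough cannot be settled from the documents; it depends on a correlation that they do not supply.

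**What to change.** Withdraw the 0.91 claim. Say how weeks 4 and 8 form the second level of the within factor, and set the repetitions to match. Compute power for the drug-by-treatment interaction, or for a baseline-adjusted comparison if the analysis is changed to one. Show the result over a stated range of rho, labelled as an assumption unless a source is cited; the table in the working is an illustration, to be recomputed once the visits are defined.

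State plainly that 10 subjects per sub-study reach 0.9 only at high correlation: above about 0.83 with one post visit, or about 0.77 with the mean of two under the assumptions given. If such a value cannot be supported, the requested power of 0.9 should be dropped openly.

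The cost is a revised power paragraph and table, and a less favourable stated power. The sample size need not change.
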